1.0 OBJECTIVES AND STUDY ENDPOINTS

Primary endpoint

1. Determine the overall response rate (complete remission plus partial remission) in Richter transformation (RT) after 2 courses of blinatumomab, ibrutinib and nivolumab treatment.

Secondary endpoints

1. Assess the safety and feasibility of administering blinatumomab combined with ibrutinib and nivolumab to patients with RT.
2. Determine the complete remission rate for RT after 1 and 2 courses of therapy.
3. Determine the progression-free survival rate for RT at 1 year.
4. Determine the overall survival rate for RT at 1 year.
5. Determine the proportion of patients who proceed to allogeneic stem cell transplantation as next treatment.

Exploratory objectives

1. Pre- and post-treatment (progression) tumor biopsies for immunologic analysis, including immune checkpoint expression by tumor and by infiltrating T cells, flow cytometry and RNA-sequencing analysis (including the potential to perform single cell RNA-seq) or array-based analysis of immune cell subsets.
1. Immune checkpoint expression by circulating T cells and T cell subset analysis.
2. “Liquid biopsy” using circulating tumor DNA analysis and comparison with mutational profile identified in concurrent CLL specimen and tumor biopsy. This will also be used as an MRD analysis tool.

Correlation of RT microRNA profile with response to treatment and outcomes.

2.0 BACKGROUND AND RATIONALE

2.1 Richter Transformation

RT is defined as the transformation of CLL into a more aggressive lymphoma; while this is most commonly diffuse large B cell lymphoma (DLBCL) histology, rare cases of transformation to Hodgkin Lymphoma (HL)¹ histology are recognized. A large series, comprising all newly diagnosed CLL patients seen at the Mayo Clinic over 12 years, demonstrated that 2.3% of patients subsequently

developed biopsy-proven RT, at a rate of 0.5% per year; almost half had never required treatment for CLL prior to the diagnosis of RT.² Clinicopathologic features suggestive of the diagnosis include high fever, weight loss, rapidly enlarging lymph nodes, hypercalcemia and elevated LDH.³ There is an ongoing incidence of RT seen in patients treated with highly effective, novel, targeted therapies for CLL, such as ibrutinib⁴ and venetoclax.⁵

Prognosis is determined by both genetic and clinical features. Approximately 80% of DLBCL transformations are clonally related to the underlying CLL; the 20% with clonally unrelated DLBCL have a significantly better prognosis. Clonal relationship can be determined by comparing the sequences of the *IGHV* gene of the lymphoma to that of untransformed CLL cells. Two clinical prognostic models have been developed,^{6, 7} the latter of which also demonstrated the importance of *TP53* disruption as a negative prognostic feature.

Treatment is generally unsatisfactory. Moderate to high-intensity chemoimmunotherapy regimens have produced CR rates of 5-38%, with median survival in most series of <1 year.⁸⁻¹² *TP53* disruption likely plays a major role in chemotherapy resistance. A minority of patients achieved long-term survival after allogeneic stem cell transplantation (alloSCT),⁶ but most patients are not eligible for this treatment due to age, co-morbidities, lack of appropriate donor, and/or failure to achieve a response to initial treatment. Nonetheless, long-term survival after alloSCT in a subgroup of patients suggests that immunologic control is possible. More effective therapy is urgently needed in order to increase the proportion of patients able to undergo alloSCT and to achieve more durable disease control in those patients who are not candidates for alloSCT.

2.2 Blinatumomab

Blinatumomab (BLINCYTO®) is a murine recombinant single-chain antibody construct combining both the binding specificity for the pan B cell antigen CD19 and the epsilon chain of the T cell receptor/CD3 complex on one polypeptide chain. It is monomeric, non-glycosylated, with a molecular weight of 55 kilo-Daltons (kDa). It belongs to a new class of bispecific antibody constructs called bispecific T cell engagers (BITE). Bispecific T cell engagers were designed to direct T-effector memory cells against target cells. The proximity induced by the BITE triggers target cell-specific cytotoxicity, which resembles typical cytotoxic T lymphocyte (CTL) activation. This T cell-mediated target-specific killing is the therapeutic mechanism of action of blinatumomab.^{13, 14}

Blinatumomab specifically targets cells that express CD19, a B cell-restricted surface antigen. Blinatumomab recruits and activates T cells via a lower affinity interaction with CD3 (8.7×10^{-8} M). The activated T cells then induce a half-maximal target cell lysis ranging *in vitro* between 10 to 100 pg/mL showing blinatumomab to be an extremely potent molecule.¹⁵

During the course of tumor cell elimination, activated T cells synthesize and secrete pro-inflammatory cytokines, such as tumor necrosis factor-alpha (TNF- α), interferon-gamma (IFN- γ), interleukin (IL)-6, and IL-2, which can induce symptoms such as fever or decreases of blood pressure. *In vitro* data demonstrate cytokine release as a result of blinatumomab-mediated activation, which can be attenuated by corticosteroids without impairing the cytotoxic activity. *In vivo* data indicate cytokine release to be most prominent following the first dose of blinatumomab.

2.2.1 Blinatumomab in Precursor B-cell Acute Lymphoblastic Leukemia

A large, 189 patient phase II study in precursor B cell acute lymphoblastic leukemia (B-ALL), confirmed the safety and efficacy of blinatumomab and was the basis for FDA approval in that disease. Blinatumomab was given as a continuous IV infusion (4 weeks on followed by 2 weeks off) for up to 5 cycles (cycle 1 only: 9 μ g/d days 1-7; then 28 μ g/d). Regardless of causality, the most common adverse events (AEs) were pyrexia (59%), headache (35%) and febrile neutropenia (29%). The most common grade ≥ 3 AEs were febrile neutropenia (26%), anemia (15%) and neutropenia (15%); 2% had grade ≥ 3 cytokine release syndrome. The most common grade ≥ 3 nervous system disorders were headache (4%), encephalopathy (3%) and ataxia (2%). Three (2%) pts had grade 5 AEs considered treatment-related (sepsis, n=2; candida infection, n=1).¹⁶

3.0 STUDY POPULATION

30 patients will be enrolled in this phase II study, 9 in the blinatumomab monotherapy phase and 21 in the combination phase.

3.1 Inclusion Criteria

1. Patients with previously treated CLL and biopsy-proven Richter's transformation with DLBCL histology according to IWCLL criteria (Richter Transformation – RT) AND CD19 positive by flow cytometry OR immunohistochemistry.
2. Eastern Co-operative Oncology Group (ECOG) performance status ≤2.
3. Age ≥18 years at the time of informed consent.
4. Able to provide informed consent and be willing to participate in study schedule and events.

3.2 Exclusion Criteria

1. Other active malignancy receiving systemic therapy.
2. History or presence of clinically relevant disorder affecting the CNS such as epilepsy, childhood or adult seizure, paresis, aphasia, stroke, severe brain injuries, dementia, Parkinson's disease, cerebellar disease, organic brain syndrome, or psychosis, with the exception of a history of CNS lymphoma that is controlled with intrathecal therapy.
3. Known active DLBCL in the CNS (confirmed by CSF analysis).
4. Current autoimmune disease requiring >/= 20mg/day of prednisone or systemic immunosuppressive therapy (eg. With cyclosporine or azathioprine).
5. Allogeneic HSCT within 24 weeks before the start of protocol-specified therapy.

6. Active Graft-versus-Host Disease (GvHD), grade 2-4 according to the Glucksberg criteria, active chronic GvHD requiring systemic treatment or requirement for systemic GvHD prophylaxis with cyclosporine or tacrolimus.
7. Cancer chemotherapy within 2 weeks before start of protocol-specified therapy, with the exception of intrathecal chemotherapy, dexamethasone, and oral small molecule inhibitors such as BTK-inhibitor, PI3K-inhibitor, or Bcl-2-inhibitor, which are allowed until the start of protocol-specified therapy). In addition, any subject whose organ toxicity (excluding hematologic) from prior treatment has not resolved to no more than CTCAE grade 1
8. Radiotherapy within 2 weeks before the start of protocol-specified therapy
9. Abnormal screening laboratory values as defined below:
 - ALT (SGOT) and/or ALT (SGPT) and/or ALP $\geq 5 \times$ upper limit of normal (ULN)
 - Total bilirubin $\geq 1.5 \times$ ULN, unless due to Gilbert's disease
 - Creatinine $\geq 2.0 \times$ ULN or creatinine clearance $<50 \text{ mL/min}$ (calculated)
10. Known infection with human immunodeficiency virus (HIV) or chronic infection with hepatitis B virus (HBsAg positive) or hepatitis C virus (anti-HCV positive)
11. Patient is pregnant or breast feeding
12. Woman of childbearing potential and is not willing to use 2 highly effective methods of contraception while receiving protocol-specified therapy and for an additional **5 months** after the last dose of protocol-specified therapy
13. Male who has a female partner of childbearing potential or a pregnant partner, and is not willing to use a condom during sexual activity while receiving protocol-specified therapy and for **7 months** after the last dose of protocol-specified therapy
14. Currently receiving treatment in another investigational device or drug study
15. Subject previously treated with blinatumomab
16. History or evidence of any other clinically significant disorder, condition or disease (with the exception of those outlined above) that, in the opinion of the Principal Investigator would pose a risk to subject safety or interfere with the study evaluation, procedures or completion.
17. Previously received nivolumab or other PD1 inhibitor.

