4.4 Response assessment

Formal response assessment will take place 2weeks (+/- 1 week) following completion of the first course of blinatumomab.. Response assessment will comprise laboratory evaluation (CBC), bone marrow examination and PETCT scan. Responses in RT for the primary study endpoint will be assessed according to the Lugano criteria¹⁹ and, as an exploratory endpoint, in co-existing CLL, according to 2018 IWCLL response criteria. Responses in RT will be assessed separately from responses in CLL. Any nodal or extranodal lesion with SUV ≥ 5.0 on PETCT will be considered indicative of RT, for the purposes of response assessment. Lesions with SUV <5.0 pre-treatment will be considered to be due to CLL, rather than RT; residual PET avidity in such lesions post-treatment will not be considered evidence of failure of control of RT, provided SUV remains <5.0 . In order for CR to be attained, all lesions with SUV ≥ 5.0 pre-treatment must be PET negative post-treatment and there must be no new PET avid lesions, unless these are proven by biopsy not to be due to Richter

Transformation. PET characterization of target lesions as due to CLL or RT pre-treatment will allow separate response assessment for RT (the primary end point) and CLL (an exploratory endpoint), without discrepancies arising due to the differences in response criteria. When possible, biopsy of residual RT sites will be requested to evaluate for residual disease.

Please note that there may be instances where PETCT is not able to be performed. In these instances, CT scan will be performed instead (see section 8.0 and 9.0)

A second response assessment will be undertaken 4 weeks (+/-1 week) after completion of the consolidation cycle.

4.5 Allogeneic stem cell transplantation.

In patients where a suitable donor is identified and who are considered eligible, allogeneic stem cell transplantation may be offered any time after completion of the first cycle of blinatumomab and initial response assessment. Patients will be considered “off study” on the date they commence pre-transplant conditioning chemotherapy. If the patient agrees, they will be enrolled on a departmental umbrella protocol (DR09-0223) to continue to follow them for overall survival.

4.6 Surveillance after completion of blinatumomab.

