8.0 PRE-TREATMENT EVALUATION

Pre-treatment evaluation is outlined in table 3.

Table 3. Pre-treatment evaluation

Pre-treatment evaluation is outlined in table 3, below. Further explanation for the specific tests ordered is provided in table 4, contained within section 9.

Procedure	Schedule
Informed consent	Within 30 days of therapy
Medical history	Within 14 days of therapy
Complete physical examination including vital signs	Within 14 days of therapy
Complete neurologic exam	Within 14 days of therapy
Document concomitant medications	Within 14 days of therapy
Hematology	Within 14 days of therapy
Biochemistry	Within 14 days of therapy
Bone marrow aspirate and biopsy	Within 60 days of therapy
CLL prognostic marker evaluation on bone marrow (FISH, using probes for ATM (11q22.3), D12Z3 (12cen), D13S319 (13q14.3), LAMP1 (13q34), p53 (17p13.1); stimulated metaphase cytogenetics; next generation sequencing (NGS) panel for CLL-associated mutations, including TP53 (see below for details); IGHV mutational status and VH utilization (this does not need to be repeated if previously performed at M.D. Anderson); flow cytometry, including CD38. Please note tests can be done on peripheral blood if a bone marrow sample is not available. Additionally, some patients with Richter Transformation may not have sufficient CLL cells in bone marrow or blood to perform this testing. Not performing these tests will therefore not be considered as deviations.	Within 60 days of therapy
PETCT scan. If PETCT cannot be done for logistic reasons, CT scan of the neck, chest, abdomen and pelvis will be performed instead.	Within 28 days of therapy
Lymph node biopsy (or pathology review of recent biopsy material). If a lymph node biopsy consistent with Richter Transformation was performed outside this window and PETCT shows changes consistent with Richter Transformation, biopsy does not need to be repeated. Pathology review for out-of-window biopsies does not need to be performed if the diagnosis was made originally at M.D. Anderson.	Within 28 days of therapy
Prognostic marker evaluation on lymph node biopsy material. Where possible, this will include CLL FISH panel or array cGH, unstimulated and stimulated metaphase cytogenetics, IGHV mutational status and VH utilization and NGS panel	
Pregnancy test	Within 7 days of therapy
Immunologic evaluation, if patient consents to correlative studies	Within 14 days of therapy

Tissue banking	Within 28 days of therapy

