9.0 EVALUATION DURING TREATMENT

Table 4: evaluation which will take place pre-treatment and during the study

Assessment	Base-line(1)	Cycle 1				Response assess	Cycle 2						Response assess	Ibrutinib + nivolumab consolidation (q4w for 36 weeks from 2 nd response assessment)	Surveillance (2)	At progression/ End-of-study
Day within cycle(3)	-28 to 1	1	15-31	36	43	57 (+/- 1 week)	1-3	8	15	22	29	43	57 (+/- 1 week)			
Informed consent(4)	X															
Medical history(5)	X	X	X	X	X	X	X	X	X	X	X	X	X	X	q12w	X
Physical examination(6)	X	X	X	X	X	X	X	X	X	X	X	X	X	X	q12w	X
Neurological examination(7)	X	X	X	X	X		X	X	X	X	X					
Concomitant medications(8)	X	X	X	X	X		X	X	X	X	X	X		X	q12w	X
CBC with differential(9)	X	X	X	X	X	X	X	X	X	X	X	X		X	q12w	X
Bio-chemistry(10)	X	X	X	X	X	X	X	X	X	X	X	X	X	X	q12w	X
Thyroid function(11)	X	q4 w														
Bone marrow(12)	X					X							X			X
PETCT scan(13)	X					X							X	q12 weeks	q24w	X
Lymph node biopsy(14)	X															X
Pregnancy test(15)	X															X
NGS panel(16)	X															X
Immunologic evaluation(17)	X															X
Tissue banking(18)	X															X
ctDNA(19)	X					X							X	At completion of nivolumab		X
Saliva (20)	X															

¹Baseline/screening testing. This must be performed within the timeframes outlined in table 3.

²Surveillance. Patients will have routine history and physical examination, CBC, routine biochemistry approximately every 12 weeks and a PETCT scan or CT scan with and without IV contrast approximately every 24 weeks (+/- 4 weeks) after completing ibrutinib + nivolumab consolidation, until 2 years after initiation of therapy, until relapse, allogeneic stem cell transplantation, or initiation of salvage therapy, whichever occurs first. Patients who have not proceeded to allogeneic

transplantation and who remain in remission at the end of the study, and those who proceed to transplant, will be enrolled on a departmental umbrella protocol (DR09-0223) to follow them for overall survival.

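### The baseline PETCT/CT may predate a patient's last prior anti-lymphoma treatment, so shrinkage from that treatment can count towards the RT response rate

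*Combined protocol and SAP*

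**What the plan says.** **Prior treatment.** Section 3.2 item 7 excludes "Cancer chemotherapy within 2 weeks before start of protocol-specified therapy", and item 8 excludes "Radiotherapy within 2 weeks before the start of protocol-specified therapy". Item 7 exempts intrathecal chemotherapy, dexamethasone and oral BTK, PI3K and Bcl-2 inhibitors, "which are allowed until the start of protocol-specified therapy". Table 1 also provides for dexamethasone during screening in patients with large or fast-growing disease, leaving dose and duration to the investigator.

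**Baseline scan.** The PETCT row of Table 3 (section 8.0), with CT as the substitute, reads "Within 28 days of therapy". Table 4 footnote 1 (section 9.0) says of baseline testing: "This must be performed within the timeframes outlined in table 3". Footnote 13 places the scan in the screening period. Neither table links it to the date of the last prior treatment.

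**Use of the scan.** Section 4.4 states: "In order for CR to be attained, all lesions with SUV ≥ 5.0 pre-treatment must be PET negative post-treatment". The same scan sorts lesions into RT (SUV of 5.0 or more) and CLL (below 5.0). In Appendix H a PET-based partial response needs uptake lower than at baseline, and a CT-based one needs a fall of at least 50% in the summed lesion products.

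**Rules that bear on the interval.** Section 7.2 prohibits chemotherapy, other lymphoma or leukemia treatment, and radiotherapy (apart from localized treatment of another cancer) while on study. Table 4 footnote 4 dates participation from signature of the consent form and bars protocol-specific procedures before it.

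**The concern.** A change from baseline measures the effect of study treatment only if nothing else active was given after the baseline was taken. Here the scan window is twice the exclusion window for chemotherapy and radiotherapy, and some active drugs have no exclusion window. A patient scanned early and then treated before day 1 would be judged against a picture of disease that the earlier treatment may already have altered.

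The stake is the primary endpoint. The trial has a single arm and section 14.0 reads its ORR against 43% from an earlier ibrutinib plus nivolumab study, so no concurrent control would show the carry-over. The same responses feed the CR rates and the response stopping rule.

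**Working it through.** **1. The windows.** Inputs: scan limit 28 days (Table 3); exclusion period 14 days (section 3.2, items 7 and 8); exempt drugs 0 days (item 7).
- Chemotherapy or radiotherapy: a scan on day -28 followed by treatment on days -27 to -15 satisfies both rules. That is 27 - 15 + 1 = 13 days, or 14 if day -14 itself is taken as permitted.
- Exempt drugs: they may be given from the scan to the start, so up to the full 28 days.
- Days -14 to -1 are already free of chemotherapy and radiotherapy, so a scan that meets every current rule and follows both is always possible.

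**2. Is there a linking rule?** Sections 3.1, 3.2, 4.4, 8.0 and 9.0 and Appendix H contain no requirement that the scan follow the last prior treatment, be repeated after bridging treatment, or show progression after it. Table 3 sets only an outer limit of 30 days for consent. A patient may therefore be scanned routinely on day -28, treated before day -14, and consented afterwards.

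**3. Does it reach the endpoint?** On the planned schedule the second assessment falls on day 57 of the second 8-week cycle, which is day 56 + 57 = 113. A lesion that lost uptake before day 1 and then stayed unchanged would still show lower uptake than at baseline on day 113. With no new lesions, that meets the PET-based partial response rule.

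**4. The plan's own figure.** With the beta(0.8, 1.2) prior and x responses in 21, the posterior is beta(0.8 + x, 1.2 + 21 - x). For x = 13 this is beta(13.8, 9.2), whose equal-tailed 90% interval is 0.430 to 0.760, width 0.329. Section 14.0 states a width of 0.33 and a lower limit matching 43%, so the figure reproduces. The stopping boundaries and all 16 early-stopping probabilities also reproduce within 0.01.

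**5. Sensitivity to misattributed responses.** Suppose 13 responses are observed and k of them are carry-over. Each is worth 1/21 = 4.8 percentage points.

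| k | responses due to study treatment | 90% interval | P(ORR > 0.43) |
|---|---|---|---|
| 0 | 13/21 | 0.430 to 0.760 | 0.95 |
| 1 | 12/21 | 0.387 to 0.721 | 0.89 |
| 2 | 11/21 | 0.344 to 0.681 | 0.79 |
| 3 | 10/21 | 0.303 to 0.639 | 0.64 |

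**6. Sensitivity by assumed rates.** Let a fraction f of patients be treated between scan and day 1, and let a proportion c of their would-be non-responses be counted as responses. The apparent rate is p + (1 - p) × f × c. With p = 0.43 and no carry-over, the binomial probability of at least 13/21 is 0.064.
- f = 0.10, c = 0.25: apparent rate 0.43 + 0.57 × 0.025 = 0.444; probability 0.082.
- f = 0.25, c = 0.50: 0.43 + 0.57 × 0.125 = 0.501; probability 0.195.
- f = 0.50, c = 0.50: 0.43 + 0.57 × 0.25 = 0.573; probability 0.421.

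For the response boundary alone, the chance of stopping early is 0.429 at an apparent rate of 0.30 and 0.278 at 0.35. The values of f and c are assumptions, because the documents give neither.

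**The case against.** **Section 7.2 may already close the interval.** If the study runs from consent (footnote 4) and the scan belongs to screening (footnote 13), chemotherapy or RT-directed radiotherapy after a post-consent scan is prohibited. This has force: for those treatments it leaves mainly the routine pre-consent scan accepted as baseline. It does not close the gap. Section 7.2 also prohibits other leukemia and lymphoma drugs, yet item 7 permits oral inhibitors until the start, so the prohibition cannot plainly run from consent. Its steroid restriction begins only with blinatumomab.

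**The endpoint is late.** By about day 113, treatment given on days -27 to -15 is some 18 to 20 weeks old. Carry-over is indeed more plausible at the first assessment. But earlier shrinkage need only be held, not deepened, to count as a partial response.

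**The direction is not proven.** In fast-growing disease an old scan understates the burden on day 1, which makes response harder to show. This stands. So does the point that the benchmark study's own scan windows are not in the text available, so the net bias against 43% is unknown.

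**The marrow.** Table 3 also has "Bone marrow aspirate and biopsy Within 60 days of therapy", and a reader might infer a wider gap there. The documents show no route from that window to an inflated RT response. PET-based response uses marrow FDG uptake, CT-based CR requires normal morphology at assessment and not a change from baseline, and the CLL response is exploratory.

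**Re-timing can do harm.** A scan after bridging treatment could show a treated RT lesion below SUV 5.0, which section 4.4 would then assign to CLL. This is correct, and the fix has to deal with it.

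**Conclusion.** The concern holds in a limited form. The plan accepts a baseline scan that predates prior treatment, and its response rules would then credit the combination with that treatment's effect. For chemotherapy and radiotherapy the exposure is about 13 days and arises mainly where a pre-consent scan serves as baseline. For screening dexamethasone or a newly started oral inhibitor it is up to 28 days.

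A reader might infer that the ORR will be inflated, or by a known amount. The documents do not support that: they do not say how many patients would be affected, and growth before day 1 acts the other way. The tables above show how little misattribution the design tolerates and are not a forecast. They rest on the planned 13/21, the stated prior and, in step 6, assumed rates with no allowance for early stopping. The chemoimmunotherapy CR rates of 5-38% in section 2.1 come from regimens of moderate to high intensity and do not measure what treatment in this short interval would achieve.

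This is a worthwhile, inexpensive improvement to how the primary endpoint is measured. It is not a defect that invalidates the design.

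**What to change.** 1. In Table 3 and Table 4 footnote 13, state that the baseline PETCT/CT is done after the last dose of chemotherapy and the last fraction of radiotherapy, still within 28 days of the start.
2. In section 4.4, keep the RT label for any lesion with SUV of 5.0 or more on an earlier available scan, so that re-timing does not turn partly treated RT into CLL.
3. Do not count a lesion irradiated after the baseline scan as an RT target.
4. In section 14.0, report the ORR also without patients who had any anti-lymphoma treatment between the baseline scan and cycle 1 day 1, including screening dexamethasone or a newly started oral inhibitor. The re-timing rule does not reach these drugs, so this analysis is the safeguard for them.

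The cost is a few sentences and tighter scan scheduling. Occasionally a clinical scan taken before bridging treatment could not serve as baseline, and the study scan would have to fit into days -14 to -1. The extra analysis needs only dates of prior and concomitant treatment, which footnotes 5 and 8 already have recorded. The sample size stays at 21, and no exclusion period or treatment rule changes.
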